13.13.5. Efficacy Tables

Efficacy: Tables					
No.	Population	IDSL / TST ID / Example Shell	Title	Programming Notes	Deliverable
Primary Efficacy Analyses					
2.1	ITT-E	Shell TPEF1	Summary of Analysis for Proportion of Subjects with Plasma HIV-1 RNA ≥ 50 c/mL at Week 48 (Maintenance Phase) – Snapshot Analysis – ITT-E		HL, WK48
2.2	Per-Protocol	Shell TPEF1	Summary of Analysis for Proportion of Subjects with Plasma HIV-1 RNA ≥ 50 c/mL at Week 48 (Maintenance Phase) – Snapshot Analysis - PP		WK48
2.4	ITT-E	Shell TPEF2	Summary of Study Outcomes (≥ 50 c/mL) at Week 48 (Maintenance Phase) – Snapshot Analysis		HL, WK48
2.5	ITT-E	Shell TPEF3	Treatment by Strata Tests of Homogeneity for Proportion of Subjects with Plasma HIV-1 RNA ≥ 50 c/mL at Week 48 (Maintenance Phase) - Snapshot Analysis		WK48
2.6	ITT-E	Shell TPEF4	Summary of Analysis for Proportion of Subjects with Plasma HIV-1 RNA ≥ 50 c/mL at Week 48 by Subgroup (Maintenance Phase) - Snapshot Analysis		WK48
2.7	ITT-E	Shell TPEF5	Summary of Study Outcomes (≥ 50 c/mL) at Week 48 by Subgroup (Maintenance Phase) – Snapshot Analysis		WK48
Secondary Efficacy Analyses					
2.8	ITT-E	Shell TPEF1	Summary of Analysis for Proportion of Subjects with Plasma HIV-1 RNA < 50 c/mL at Week 48 (Maintenance Phase) – Snapshot Analysis – ITT-E		HL, WK48
2.9	Per-Protocol	Shell TPEF1	Summary of Analysis for Proportion of Subjects with Plasma HIV-1 RNA < 50 c/mL at Week 48 (Maintenance Phase) – Snapshot Analysis - PP		HL, WK48
2.10	ITT-E	Shell TPEF3	Treatment by Strata Tests of Homogeneity for Proportion of Subjects with Plasma HIV-1 RNA < 50 c/mL at Week 48 (Maintenance Phase) - Snapshot Analysis		WK48

Efficacy: Tables					
No.	Population	IDSL / TST ID / Example Shell	Title	Programming Notes	Deliverable
2.11	ITT-E	Shell TPEF4	Summary of Analysis for Proportion of Subjects with Plasma HIV-1 RNA <50 c/mL at Week 48 by Subgroup (Maintenance Phase) - Snapshot Analysis		WK48
2.12	ITT-E	Shell TSEF2	Proportion of Subjects with Plasma HIV-1 RNA \geq 50 c/mL by Visit (Maintenance Phase) – Snapshot Analysis		WK48
2.13	ITT-E	Shell TSEF2.1	Proportion of Subjects with Plasma HIV-1 RNA \geq 50 c/mL by Subgroup and Visit (Maintenance Phase) – Snapshot Analysis		WK48
2.14	ITT-E	Shell TSEF7.0	Summary of Kaplan-Meier Estimates of Proportion of Subjects Without Confirmed Virologic Failure by Week 48 during Maintenance Phase - Treatment Related Discontinuation = Failure		WK48
2.15	ITT-E	Shell TSEF7.1	Summary of Kaplan-Meier Estimates of Proportion of Subjects Without Confirmed Virologic Failure by Week 48 during Maintenance Phase - Efficacy Related Discontinuation = Failure		WK48
2.16	ITT-E	Shell TSEF2	Proportion of Subjects with Plasma HIV-1 RNA <50 c/mL by Visit (Maintenance Phase) – Snapshot Analysis		WK48
2.17	ITT-E	Shell TSEF2	Proportion of Subjects with Plasma HIV-1 RNA <50 c/mL by Subgroup and Visit (Maintenance Phase) – Snapshot Analysis		WK48
2.18	ITT-E	Shell TSEF2	Proportion of Subjects with Plasma HIV-1 RNA <200 c/mL by Visit (Maintenance Phase) – Snapshot Analysis		WK48
2.19	ITT-E	Shell TSEF9	Proportion of subjects with HIV-1 RNA \geq 50 c/mL at Week 48 (Snapshot) by Last Delay in IP Injection (Maintenance Phase)	For Q4W IM arm only. The last delay in IP injection is the delay in IP injection at Week 48, or delay in last IP injection prior to Week 48 if a subject has no injection at WK48 (e.g. missing visit or early withdrawal)	WK48,
2.20	ITT-E	Shell TSEF8	Summary of Plasma HIV-1 RNA by Visit		WK48, 96, EOS

CONFIDENTIAL

201585

Efficacy: Tables					
No.	Population	IDSL / TST ID / Example Shell	Title	Programming Notes	Deliverable
2.21	ITT-E	Shell TSEF3	Proportion of Subjects Meeting Confirmed Virologic Failure Criteria by Visit (Maintenance Phase)		HL, WK48
2.22	ITT-E	Shell TSEF3	Proportion of Subjects Meeting Confirmed Virologic Failure Criteria by Visit for Q4W Arm Only (Maintenance + Extension Phase)		WK96, EOS
2.23	ESP	Shell TSEF3	Proportion of Subjects Meeting Confirmed Virologic Failure Criteria by Visit for Current ART Arm Only (Extension Phase)		WK96, EOS
2.24	CVF	Shell TSEF4	Summary of Plasma HIV-1 RNA Results at Suspected and Confirmation of Confirmed Virologic Failure – Maintenance phase		WK48
2.25	ITT-E	Shell TSEF5	Summary of Change from Baseline in CD4+ Cell Count (cells/mm ³) by Visit (Maintenance Phase)		WK48, 96, EOS
2.26	ITT-E	Shell TSEF5	Summary of CD4+ Cell Count (cells/mm ³) by Visit (Maintenance Phase)		WK48, 96, EOS
2.27	ITT-E	Shell TSEF5	Summary of CD8+ Cell Count (cells/mm ³) by Visit (Maintenance Phase)		WK48, 96, EOS
2.28	ITT-E	Shell TSEF5	Summary of Change from Baseline in CD8+ Cell Count (cells/mm ³) by Visit (Maintenance Phase)		WK48, 96, EOS
2.29	ITT-E	Shell TSEF5	Summary of CD4+/CD8+ Ratio Cell Count (cells/mm ³) by Visit	While both CD4+ and CD8+ are available on the same date	WK48, 96, EOS
2.30	ITT-E	HIV1/Shell TSEF 6.0	Summary of Post-Baseline HIV-1 Associated Conditions Including Recurrences (Maintenance Phase)		WK48
2.31	ITT-E	HIV1/Shell TSEF 6.0	Summary of Post-Baseline HIV-1 Associated Conditions Excluding Recurrences (Maintenance Phase)		WK48
2.32	ITT-E	HIV2/Shell TSEF6.1	Summary of Post-Baseline HIV-1 Disease Progressions (Maintenance Phase)		WK48
2.34	ITT-E	Table 7.1026 (Latte2/week48idsl)/ Shell TSEF12	Proportion of Subjects with Plasma HIV-1 RNA <2 copies/mL by Visit - Observed Case Analysis		WK48

Efficacy: Tables					
No.	Population	IDSL / TST ID / Example Shell	Title	Programming Notes	Deliverable
2.36	ITT-E	Shell TPEF2	Summary of Study Outcomes (≥ 200 c/mL) at Week 48 (Maintenance Phase) – Snapshot Analysis		WK48
2.37	ITT-E	Shell TSEF11	Summary of Subjects per Viral Load Category by Visit (Maintenance Phase)		Wk48
2.38	ITT-E	Shell TSEF5	Summary of Change from Baseline in CD4+ Cell Count (cells/mm ³) at Week 48 by Subgroup (Maintenance Phase)		WK48

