To assess viral resistance in participants experiencing confirmed virologic failure (CVF)	
 Incidence of treatment emergent genotypic and phenotypic resistance to CAB, RPV and other on-study ART through Week 48
To assess the impact of Baseline third agent treatment class (INI, NNRTI, or PI) on efficacy, safety, tolerability, and viral resistance of CAB LA + RPV LA compared to continuation of current ART	
By Baseline third agent treatment class:
 
 Proportion of participants with a 'virologic failure' endpoint as per FDA Snapshot algorithm at Week 48 (Intent-to-Treat Exposed [ITT-E] population). Proportion of participants with Plasma HIV-1 RNA <50 c/mL at Week 48 using the FDA Snapshot algorithm (Intent-to-Treat Exposed [ITT-E] population) Incidence and severity of select AEs and laboratory abnormalities over time including Week 48 Proportion of participants who discontinue treatment due to AEs over time including Week 48 Absolute values and changes in select laboratory parameters over time including Week 48 Incidence of observed genotypic and phenotypic resistance to current antiretroviral regimen and to CAB or RPV for participants meeting confirmed virologic failure (CVF)
To characterize CAB and RPV concentrations and population pharmacokinetics and identify important determinants of variability.	
 Plasma PK parameters for CAB LA and RPV LA (when evaluable, C_{trough}, concentrations post dose [$\sim C_{max}$], and area under the curve [AUC]) Demographic parameters including, but not limited to, age, sex, race, body weight, body mass index, and relevant laboratory parameters will be evaluated as potential predictors of inter- and intra-participant variability for pharmacokinetic parameters

To evaluate the antiviral and immunologic effects, safety, tolerability, and viral resistance of CAB LA + RPV LA for participants during the Extension Phase
 
 For participants randomized to CAB LA+ RPV LA at Day 1 For participants electing to 	
 Proportion of participants with plasma HIV-1 RNA < 50 c/mL over time including Week 96 (observed case) Proportion of participants with confirmed virologic failure (two consecutive plasma HIV-1 RNA levels ≥ 200 c/mL after prior suppression to <200 c/mL)

Objectives	Endpoints

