Design Features	
 Phase III, randomized, open-label, active-controlled, multicenter, parallel-group, non-inferiority study designed to assess the antiviral activity and safety of a two-drug regimen of CAB LA + RPV LA compared with maintenance of current ART The ATLAS study comprises a Screening Phase (up to 35 days), a Maintenance Phase (Day 1 to Week 52), and the randomized portion of the study will continue with an Extension Phase up to at least 96 weeks. Additionally, any participant who receives at least a single dose of CAB LA and/or RPV LA and discontinues the CAB LA + RPV LA regimen will enter the Long-term Follow-up Phase and will initiate highly active antiretroviral therapy (HAART) for at least 52 weeks after the last dose of CAB LA and/or RPV LA
Dosing	
 Maintenance Phase: 1:1 randomization to continue current ART or be switched to the CAB LA + RPV LA regimen through 52 weeks Extension Phase: CAB LA + RPV LA
Treatment Assignment	
 N =570 randomized at start of Maintenance Phase At Week 52, participants randomized to continue on current ART will have the option to either continue study participation by switching to CAB LA + RPV LA in the Extension Phase, or to complete their study participation at

Overview of Study Design and Key Features	
	Week 52. 
 • GSK RandAll NG used to generate randomization schedules • Stratified Randomization by baseline third agent class (PI, INI, or NNRTI) and sex at birth.
Interim Analysis	
 • 50% of subjects completing Week 24 • Continuous time monitoring of confirmed virologic failure (CVF) (both in the NNRTI strata and overall) • The main analysis will be conducted to evaluate the primary objective of the protocol at Week 48. • Further data cuts and analyses may be conducted as necessary in order to support regulatory submissions and publications.

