PK Population	
 All participants who receive CAB and / or RPV and undergo PK sampling during the study, and provide CAB and /or RPV plasma concentration data. 	
 PK
Confirmed Virologic Failure	Comprised of all subjects in the ITT-E population who met Confirmed Virologic Failure (CVF)	
 Genotypic Phenotypic

Population	Definition / Criteria	Analyses Evaluated
(CVF) Population	criteria. *CVF is defined as: Rebound as indicated by two consecutive plasma HIV-1 RNA levels ≥ 200 c/mL after prior suppression to < 200 c/mL	
 IDMC CVF Analysis
Futility Analysis Population at Week 24	
 Comprised of all subjects in the ITT-E population and who started study treatment at least 169 days prior to the IDMC cut-off date (in order to account for subjects who withdrew early but would have achieved Week 24) 	
 IDMC Futility Analysis

NOTES:

- Please refer to [Appendix 13](#): List of Data Displays which details the population to be used for each display being generated.

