13.7. Appendix 7: Reporting Standards for Missing Data

13.7.1. Premature Withdrawals

Element	Reporting Detail
General	
 ● Subject study completion (i.e. as specified in the protocol) was defined as: 
 ○ Randomly assigned to either treatment group, completed the randomized Maintenance Phase including the Nominal Week 52 visit, and did not enter the Extension Phase; ○ Randomly assigned to either treatment group, completed the randomized Maintenance Phase including the Nominal Week 52 visit, and entered and completed the Extension Phase (defined as remaining on study until transitioning to ATLAS-2M, or commercial supplies of CAB LA + RPV LA become locally available, or development of CAB LA + RPV LA is terminated). 
Participants who withdraw from CAB LA + RPV LA and go into the Long-Term Follow Up Phase will be considered to have prematurely withdrawn from the study, even if they complete the 52-week follow-up phase. In addition to the 52 week Long-Term Follow-Up Phase required for participants randomized to CAB LA + RPV LA, an in-clinic Follow-Up visit will be conducted approximately 4 weeks after the last dose of study medication for participants randomized to the Current ART arm with ongoing AEs, SAEs, and also any laboratory abnormalities that are considered to be AEs or potentially harmful to the participant, at the last on-study visit. Assessments at the Follow-up visit should reflect any ongoing complaints (e.g., blood draws to follow a laboratory abnormality). Follow-Up visits are not required for successful completion of the study.
 
 ● Withdrawn subjects were not replaced in the study. ● All available data from participants who were withdrawn from the study will be listed and all available planned data will be included in summary tables and figures, unless otherwise specified. ● Withdrawal visits will be slotted as per Appendix 3: Assessment Windows or will be summarised as withdrawal visits.

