13.11. Appendix 11: Snapshot Algorithm Details

Detailed Algorithm Steps

- Consider an analysis visit window for Week X (e.g. Week4, ...Week 24, Week 48 et al). The Window for Week 24/48 visit is defined in Table 11 (e.g. window for Week 48 is ± 6 Week: $295 \leq \text{Study Day} \leq 378$) and in Table 9 for other visits through to Nominal Week 52 at Maintenance Phase. The Snapshot Analysis at post Maintenance Phase will not be appropriate because a large portion of responders will be switched to other studies and not all subjects would have the chance to reach same timepoint.
- The HIV1-RNA threshold of 50, 200 copies/mL will be analysed, respectively, in this study
- The analysis window 'Week 48' and HIV1-RNA threshold of '50 copies/mL' are used for the purpose of illustration. A subject's Snapshot response and reason at Week 48 are categorized as below.
 - HIV1-RNA < 50 copies/mL
 - HIV1-RNA ≥ 50 copies/mL
 - Data in window not below 50
 - Discontinued for lack of efficacy
 - Discontinued for other reason while not below 50
 - Change in background therapy*
 - No Virologic Data at Week 48 Window
 - Discontinued study due to AE or death
 - Discontinued study for other reasons
 - On study but missing data in window

* Note: since changes in ART are not permitted in this protocol, all such subjects who change ART during the maintenance phase will be considered 'HIV1-RNA ≥ 50 copies/mL'. if the change in ART is made prior to an analysis timepoint. Subjects with protocol permitted oral bridging treatment will not be considered ' HIV1-RNA ≥ 50 copies/mL' due to 'change in ART'.

- The steps in determining response and reasons are indicated in Table below, in the order stated.

Detailed steps		
Please note that the following scenarios will NOT be penalized Per Snapshot algorithm (i.e. please excluding these scenarios from Condition 1-4).		

 • Dose reduction, dropping a component, or change in formulation (e.g. 'Tivicay + Kivexa' to 'Triumeq' with the identical ingredients) 		
Condition ('Week 48' indicates Week 48 window)	Response	Reasons
1. If non-permitted change in background therapy prior to Week 48	HIV1-RNA ≥ 50	Change in background therapy
2.If permitted change ^[a] in background therapy prior to Week 48 AND the latest on-treatment VL prior to/on the date of change is ≥ 50 c/m (NA to this study)	HIV1-RNA ≥ 50	Change in background therapy

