13.13.15. Virology Tables

For Week 96/EOS IA, each display will be split into two Tables, one for Maintenance+Extension phases for Q4W arm only, and one for Extension phase for Current ART arm only)					
No.	Population	IDSL / TST ID / Example Shell (mock up below from study 200056\wk48idsl)	Title	Programming Notes	Deliverable
Genotype					
8.1	CVF	Table 9.1001	Summary of the Prevalence of Known INI Resistance Mutations at time of CVF (Maintenance phase) – Plasma Sample	(identify known INI resistance mutation per Section 13.6.6). need to add small 'n' for actual no. of subjects included in the analysis. The % will be based on 'n' rather than 'N'	WK48
8.2	CVF	Table 9.1003 (modify region to class)	Summary of the Prevalence of Major Resistance Mutations of NRTI, NNRTI and PI Class at time of CVF(Maintenance phase) - Plasma Sample	(identify Major Mutation of NRTI, NNRTI, PI class per Section 13.6.6). need to add small 'n' for actual no. of subjects included in the analysis. The % will be based on 'n' rather than 'N' (programming for defining class: can refer to arenv/arprod/gsk1349572/mid200304/week24/drivers/t_adpf_4001.sas	WK48
Phenotype					
8.3	CVF	Table 9.1005	Summary of Phenotype Susceptibility at time of CVF (Maintenance phase) - - Plasma Sample		WK48
8.4	CVF	Table 9.1005	Summary of Genotypic Susceptibility at time of CVF (Maintenance phase) - - Plasma Sample		WK48
8.5	CVF	Table 9.1005	Summary of Net Assessment at time of CVF (Maintenance phase) - Plasma Sample		WK48

CONFIDENTIAL

201585

For Week 96/EOS IA, each display will be split into two Tables, one for Maintenance+Extension phases for Q4W arm only, and one for Extension phase for Current ART arm only)					
No.	Population	IDSL / TST ID / Example Shell (mock up below from study 200056\wk48id sl)	Title	Programming Notes	Deliverable
8.6	CVF	Table 9.1006	Summary of Phenotype: Number of Drugs to Which Subject are Resistant at time of CVF(Maintenance phase) - Plasma Sample		WK48
8.7	CVF	Table 9.1007	Summary of Phenotypic Susceptibility to CAB and RPV at time of CVF(Maintenance phase) - Plasma Sample		WK48
8.8	CVF	Shell TV1	Summary of Viral load, Genotypic and Phenotypic data for Subjects Who Met Confirmed Virologic Failure Criteria During the Maintenance Phase		HL, WK48
8.9	CVF	Shell TV1	Summary of Viral load, Genotypic and Phenotypic data for Subjects who Met Confirmed Virologic Failure Criteria During the Extension Phase		WK48, 96, EOS

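### Two Week 96 Extension Phase virologic endpoints are not properly served: observed-case <50 c/mL has no planned result, and CVF has no at-risk denominator or censoring at rollover

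*SAP*

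**What the plan says.** Section 2.2 sets an Extension Phase objective for participants randomised to CAB LA + RPV LA and for those who switch to it. Its endpoints include "Proportion of participants with plasma HIV-1 RNA < 50 c/mL over time including Week 96 (observed case" and the proportion with CVF through Week 96.

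Section 13.11 gives up the Snapshot analysis after the Maintenance Phase because "a large portion of responders will be switched to other studies and not all subjects would have the chance to reach same timepoint". Section 13.7.1 defines completion of the Extension Phase as "remaining on study until transitioning to ATLAS-2M" (or until one of two other end points), so rollover is completion and not withdrawal.

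The displays in Section 13.13.5 are as follows.

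- Table 2.37, "Summary of Subjects per Viral Load Category by Visit (Maintenance Phase", is a Week 48 deliverable. The observed-case rule behind it, in Section 13.6.4, is also headed for the Maintenance Phase.
- Table 2.22, "Proportion of Subjects Meeting Confirmed Virologic Failure Criteria by Visit for Q4W Arm Only (Maintenance + Extension Phase", is listed on ITT-E and delivered at Week 96 and end of study. Table 2.23 is its counterpart in the ESP. Both use shell TSEF3, as does the Maintenance Phase Table 2.21, and both have blank programming notes.
- Tables 2.14 and 2.15, the Kaplan-Meier analyses of CVF with treatment-related or efficacy-related discontinuation, stop at Week 48. Appendix 15 defines their time variable for the Maintenance Phase only.

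**The concern.** The plan recognises that departures make Snapshot unsuitable after Week 52. It does not carry that reasoning over to the CVF proportion, and it does not complete the endpoint that takes the place of Week 96 Snapshot.

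A participant who moves to ATLAS-2M soon after Week 52 can no longer be observed to fail in this study. If that person stays in the denominator, the person counts as a non-failure through Week 96. A low Week 96 percentage would then partly reflect departures and not lasting suppression. The suppression endpoint, which could help a reader judge this, has no table at all beyond the Maintenance Phase.

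**Working it through.** **Part 1: tracing the <50 c/mL endpoint.** No assumed number is needed.

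1. Endpoint: observed case, over time to Week 96, both groups (Section 2.2).
2. Derivation: Section 13.6.4 defines the observed-case numerator and denominator under a Maintenance Phase heading. No Extension Phase version is given.
3. Overview: Table 4 in Section 7.2.5 lists the <50 c/mL proportion only through Week 48, by Snapshot.
4. Displays: Tables 2.8 to 2.11, 2.16, 2.17 and 2.37 and Figures 2.3 and 2.4 are the displays carrying <50 c/mL. None is delivered at Week 96. None is on the ESP.
5. Shorthand is unlikely. Where a display continues, the list says so: Table 2.20 is marked for Week 48, Week 96 and end of study, and Tables 1.27 and 3.55 carry notes on how they change at Week 96.

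The endpoint has no planned Week 96 result.

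**Part 2: the denominator of Table 2.22.** Section 4 points to the "List of Data Displays which details the population to be used for each display being generated", and that list gives ITT-E. The shell is the one used for the Maintenance Phase, where the arm total is the natural denominator. In Section 13.13.15, where another denominator is wanted, a note says so: "The % will be based on 'n' rather than 'N". Table 2.22 has no such note. The full arm is the likely reading, but it is an inference.

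**Part 3: size, if the full arm is used.** The SAP states no Week 96 figure to reproduce. Inputs:

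- Arm size: "N =570 randomized at start of Maintenance Phase", allocated 1:1, so 570/2 = 285.
- p1 = CVF risk to Week 52; p2 = risk from Week 52 to 96 in those still followed; r = share rolled over at Week 52. All three are assumptions, with rollover taken as unrelated to later CVF.

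Censored estimate = p1 + (1 − p1) × p2. Crude proportion = p1 + (1 − p1) × (1 − r) × p2.

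With p1 = 1%, p2 = 2%:

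- censored: 0.01 + 0.99 × 0.02 = 2.98%
- crude, r = 50%: 0.01 + 0.99 × 0.5 × 0.02 = 1.99%
- crude, r = 90%: 0.01 + 0.99 × 0.1 × 0.02 = 1.20%

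| p1, p2 | Censored | Crude, r = 50% | Crude, r = 75% | Crude, r = 90% |
|---|---|---|---|---|
| 1%, 1% | 1.99% | 1.50% (75%) | 1.25% (63%) | 1.10% (55%) |
| 1%, 2% | 2.98% | 1.99% (67%) | 1.50% (50%) | 1.20% (40%) |
| 2%, 1% | 2.98% | 2.49% (84%) | 2.25% (75%) | 2.10% (70%) |
| 2%, 2% | 3.96% | 2.98% (75%) | 2.49% (63%) | 2.20% (55%) |

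Brackets give crude as a share of censored. The gap runs from about 0.5 to 1.8 percentage points.

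**Part 4: precision.** With p1 = 1%, the number at risk after Week 52 is 285 × 0.99 × (1 − r), or about 141 at r = 50% and 28 at r = 90%. If no later CVF is seen, the one-sided 97.5% upper limit for p2 is 1 − 0.025^(1/n): 2.6% for 141 and 12.3% for 28, against 1.3% if all 285 were counted.

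**The case against.** The strongest reply is that the population column does not fix denominators in this SAP. Table 2.37 is also listed on ITT-E, yet its derivation counts only participants with an on-treatment viral load in the window. Table 2.22 is by visit, and shell TSEF3 is in a separate document, so it may already use the number observed. This stands as a caveat: the dilution is conditional on the denominator. It does not remove the point, because the SAP states neither an at-risk denominator nor a censoring rule for that table.

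It can also be said that departures are visible elsewhere. Disposition Tables 1.11 and 1.12 and exposure Tables 3.2 and 3.3 are delivered at Week 96. They help a careful reader but do not correct the percentage.

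Kaplan-Meier is not a clean remedy either. Those who leave are described as responders, so censoring them may be informative. That is a good reason to show both figures and not to replace one with the other.

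Three stronger readings are tempting and are not supported.

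- A reader might infer that the Extension Phase objective as a whole cannot be answered. HIV-1 RNA by visit (Table 2.20), individual profiles (Figures 2.6 to 2.9), resistance in CVF participants (Table 8.9) and safety displays are all delivered at Week 96.
- A reader might infer that CVF is understated by factors of 2 to 10. Those factors, 1/(1 − r) at 50% and 90% rollover, apply only to the increment after Week 52. Table 2.22 is cumulative, and its ratio is milder.
- A reader might carry the same dilution over to the ESP. By Section 4 that population contains only Current ART participants dosed with CAB and/or RPV in the Extension Phase, so someone who leaves at Week 52 without that dose is never in its denominator.

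**Conclusion.** The point holds for two endpoints. The missing Week 96 result for observed-case <50 c/mL follows directly from the text, for the Q4W arm and the ESP alike. The understatement of CVF through Week 96 in the Q4W arm is conditional on Table 2.22 using the ITT-E count. Given that, and provided p2 is above zero, the direction is downward, while the size rests on a rollover share and CVF risks that the SAP does not give.

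The consequence is limited. Section 3 plans no comparison between arms at Week 96, so the reporting is descriptive and the Week 48 primary conclusion does not depend on it. The change is still worth making, because one stated secondary endpoint would otherwise go unreported and another could be misread as durability.

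**What to change.** For the Week 96 and end-of-study reports:

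1. Extend the observed-case <50 c/mL derivation in Section 13.6.4, and Table 2.37, to the Extension visits of Table 10, for the Q4W arm and the ESP. Show the number observed and the number transitioned at each visit.
2. Keep the crude count in Table 2.22 and label its denominator.
3. Beside it, add a Kaplan-Meier cumulative CVF estimate through Week 96 with numbers at risk, censoring at transition to ATLAS-2M or other completion. Appendix 15 can be adapted for the time variable. Note that the censoring may be informative because those who leave are mostly responders.
4. Show numbers at risk in Table 2.23 as well, without claiming the same dilution there.

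The cost is SAP wording and reruns of programs that largely exist. The downside is that the Week 96 CVF figure is likely to look less favourable and will be less precise.
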